
confirm that the participant is eligible and appropriate for the study. After participants complete the screening procedures described above, provide their informed consent to participate, and are enrolled into the study, they will complete four study assessment visits over 24 months. The first visit or baseline visit (Month 0) will occur within approximately 2-8 weeks of bariatric surgery. Subsequent visits will occur at 6, 12, and 24 months follow-up. Follow-up assessments will occur within an approximate 8week window that includes 4 weeks on either side of the target date. The procedures to be completed in preparation for each of these visits are described below. Throughout participation in the study, participants medical records will be reviewed and data will be collected to obtain psychological diagnoses (including any psychiatric medications the participant is taking), appointment dates for the bariatric surgery program (to track progress through to surgery), and date and type of bariatric surgery. Assessment Visits Participants will complete the following assessments at baseline, and 6, 12, and 24 months after surgery. Participants whose surgery date is scheduled greater than 90 days after their baseline assessment (due to delays in scheduling surgery) may be asked to return to the clinic to complete a portion of the assessment. Participants will be asked to complete the ASA 24 hour dietary food recall and the impulsivity tasks (described above) within approximately 2-8 weeks prior to surgery in order to ensure that these data are within the appropriate time frame prior to surgery. We anticipate that this portion of this assessment will take approximately one hour to complete. If participants are willing to return to the clinic to complete these two portions of the assessment, they will be compensated \$25 for their time. Prevalence and Control of Chronic Diseases: 1) T2D will be identified using hemoglobin A1c (HbA1c) and glucose measurements obtained from fasting blood samples, and will be defined as HbA1c 6.5% and glucose 7.0 mmol/L (126 mg/dL), or use of antidiabetes medication.36 Prevalence will be calculated using number of participants with T2D as the numerator and total number of participants as the denominator. Controlled T2D, among individuals diagnosed with T2D, will be defined as HbA1c 7.0%.36 These labs are drawn as part of standard clinical care and the HbA1c and glucose results will be extracted from the EMR of enrolled participants. Participants will not be asked to have additional blood draws as part of the study. 2) Hypertension: systolic blood pressure (SBP) and diastolic blood pressure (DBP) will be measured using a Dinamap 9300XL monitor.. Using recently updated US guidelines, hypertension will be defined as SBP130 mm Hg, or DBP80 mm Hg, or use of antihypertensive medication.39 Prevalence will be calculated using number of participants with hypertension as the numerator and total number of participants as the denominator. Controlled hypertension, among individuals with hypertension, will be defined as SBP130 mm Hg and DBP80 mm Hg.39 Blood pressure is measured as part of standard clinical care. SBP and DBP will also be extracted from the medical record of enrolled participants from their preoperative testing with the bariatric surgery program as well as their postoperative follow up with the surgical team. Healthcare Utilization: This information will be extracted from electronic medical records (EMRs) for the following services: primary care, hospitalizations, and emergency room visits. Total number of visits and number of visits to each service will be calculated for all-cause, mental health, T2D, and hypertension related, separately. Duration of stay will also be assessed.41,42 Based on previous experience of the research team, over 70% of participants will receive their non-bariatric care in the TU or Penn systems during the study. Therefore, we will be able to obtain utilization records through the EMR.

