
Primary outcome variable(s)

All primary outcomes will be measured at 0, 6, 12, and 24 months postoperatively. Specific Aim 1: weight change

Secondary outcome variable(s)

All secondary outcomes will be measured at 0, 6, 12, and 24 months postoperatively. Secondary aims call for examining relationships between primary outcomes and some additional variables. These additional variables include psychosocial status, dietary intake, physical activity, prevalence and control of T2D and hypertension, health services utilization, and adherence to antidiabetes and antihypertensive medication.

Background

Bariatric surgery is an increasingly utilized treatment for the growing number of individuals with a body mass index (BMI) of 40 kg/m2 or 35 kg/m2 in the presence of obesity-related comorbidities. Early results are promising, with patients losing 20-35% of their initial body weight in the first 6-18 months after surgery and experiencing improvements in obesity-related comorbidities. These outcomes,

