
Study Design

Phase* Not applicable

Design

Observational assessment study

Study duration

The study period begins December 1, 2015 and ends November 30, 2020. Each participant will be enrolled for approximately 24-30 months. Although each participant will complete his/her study assessments within 24 months, participants may be enrolled for additional months. This extra time will become necessary if a participant is enrolled well before her scheduled surgery date (in many cases, patients receive all preoperative clearances months before their surgery date).

Resources necessary for human research protection

Describe research staff and justify that the staff are adequate in number and qualifications to conduct

the research. Describe how you will ensure that all staff assisting with the research are adequately informed about the protocol and their research related duties. Please allow adequate time for the researchers to conduct and complete the research. Please confirm that there are adequate facilities for the research.

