Individuals interested in bariatric surgery at Penn rst attend an information session at which they are provided an overview of the program. These sessions are led by [name], Co-Investigator and Director of the Bariatric Surgery Program, or one of his surgeon colleagues. Those who desire to have surgery schedule an initial consultation with a bariatric surgeon who evaluates their medical appropriateness for surgery. As recommended by the ASMBS and required by third party payers in the region, patients also undergo a psychosocial evaluation which evaluates their psychological appropriateness for surgery and identies behavioral issues that may impact their postoperative outcome. In our program, patients attend 3 to 6 monthly, preoperative weight management (MWM) sessions (the exact number is dictated by each patients insurer). Patients will meet with the research coordinator (RC) approximately 8-10 weeks before surgery at one of their MWM visits, who will introduce the study and describe its goals and requirements. Similarly, at the Temple Health Bariatric Surgery Program, participants will be introduced to the study by the RC at their pre-operative nutrition class or one of their MWM sessions. The population of Spanish-speaking patients at Temple Health is higher than that of Penns program. At Temple Health only, we will provide participants with the option of participation in the study using Spanish language forms. A Spanish consent form will be provided and these will be reviewed by a Spanish speaking Research Coordinator. All other research procedures described below will be the same as those at already approved at Penn and Temple. If patients express interest in participation, the RC will conduct a brief screen to assess eligibility. At this screening visit, candidates will meet individually with the research coordinator, who will explain the study and obtain participants informed consent. Medical history and physical information as well as the Beck Depression Inventory II, The Weight and Lifestyle Inventory, height, weight will be reviewed from the Bariatric Surgery Program. If patients meet the inclusion criteria, they will give their written informed consent to participate and will be scheduled for baseline assessments (described below) which will be coordinated with their next preoperative weight management session, if possible. Prior to this session, the RC will review the patients medical records and meet with the Principal Investigator and research team to conrm that the participant is eligible and appropriate for the study. After participants complete the screening procedures described above, provide their informed consent to participate, and are enrolled into the study, they will complete four study assessment visits over 24 months. The first visit or baseline visit (Month 0) will occur within approximately 2-8 weeks of bariatric surgery. Subsequent visits will occur at 6, 12, and 24 months follow-up. Follow-up assessments will occur within an approximate 8-week window that includes 4 weeks on either side of the target date. The procedures to be completed in preparation for each of these visits are described below. Throughout participation in the study, participants medical records will be reviewed and data will be collected to obtain psychological diagnoses (including any psychiatric medications the participant is taking), appointment dates for the bariatric surgery program (to track progress through to surgery), and date and type of bariatric surgery.

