
Discounting Task (DDT): participants choose between a smaller reward available immediately (e.g., \$20 today) and a larger reward available after a longer delay (e.g., \$40 in a month). People differ in their degree of delay discounting, the extent to which they forgo larger monetary magnitudes in the future in order to obtain immediate rewards. As in previous work, the immediate reward will be fixed and the magnitude and delay of the larger, later reward will vary from trial to trial. Participants will make 51 choices. The primary outcome will be the subjects discount rate, which will be estimated by fitting a logistic regression that assumes a persons decisions are a stochastic function of the difference in subjective value between the two options.127 Keeping with standard behavioral findings128,129 we will assume that subjective value (SV) is a hyperbolic function of the reward amount (A) and delay (D): SV = A/(1+kD), where k is the participants discount rate. Larger values of k indicate a greater degree of discounting future rewards. A composite measure of impulsivity will be calculated by averaging individual z-scores derived from the SST, Stroop interference score, and k-value. We predict that higher levels of impulsivity indicating poor response inhibition and greater discounting of future rewards (i.e., slower SST, higher Stroop interference score, and higher k-values) will be associated with less weight loss 24 months following bariatric surgery. Psychopathology: Psychopathology measures will be administered via interview or questionnaire at the following time points: baseline and 6, 12, and 24 months after surgery. The tasks are: Structured Clinical Interview for the DSM-5, Research Version (SCID-5-RV)129 is a semistructured interview for making DSM-5 diagnoses for mood, anxiety, eating, substance use, and psychotic disorders. A trained clinician or mental health professional who is familiar with the DSM-5 classification and diagnostic criteria administers the measure, which takes about 2.5 hours. Beck Depression Inventory-II (BDI-II)130: survey used to measure mood. It is the most widelyused measure of depressive symptomatology. Alcohol Use Disorders Identification Test (AUDIT)164: assesses the presence of alcohol use disorders before and after surgery. The Drinker Inventory of Consequences131 is a self-administered 50-item questionnaire designed to measure adverse consequences of alcohol use in five areas: Interpersonal, Physical, Social, Impulsive, and Intrapersonal. Each scale provides a lifetime and past 3-month measure of adverse consequences, and scales can be combined to assess total adverse consequences. The Fagerström Nicotine Tolerance Questionnaire132 is an 8-item, self-report designed to measure physical dependence to nicotine. Urine Drug Screens: collected in temperature sensing cups to ensure valid samples. Urines will be tested for common drugs of abuse (cocaine, opiates, amphetamines, methamphetamine, marijuana). A composite measure of psychopathology will be calculated by averaging individual z-scores derived from the presence/absence of DSM diagnoses, the BDI-II score, and the substance use measures. We predict that higher levels of psychopathology will be associated with less weight loss 24 months following bariatric surgery. Eating Behavior: Eating behavior measures will be administered via interview or questionnaire at the following time points: baseline and 6, 12, and 24 months after surgery. Total administration time is approximately 30 minutes. The tasks are: The Eating Inventory134: 51-item self-report inventory that measures three factors related to eating behavior: 1) cognitive restraint, 2) disinhibition, and 3) hunger. Eating Disorders Examination-Bariatric Surgery Version135: Identical to the widely-used Eating Disorders Examination but also measures eating disturbances specific to bariatric surgery by adding specific questions regarding dumping, plugging, chewing and spitting, and vomiting. (Note. The diagnosis of BED will be established from the SCID interview. The results of the EDE-BSV will be used as a continuous variable in the analyses described below.) Night Eating Questionnaire (NEQ)127: 14-item scale that measures symptoms of night eating and has been used in bariatric populations previously. Yale Food Addictions Scale136: 25-item mixed response scale that is used to identify those who are using high sugar/high fat foods in ways similar to symptoms that are markers of substance use, such as tolerance, withdrawal, and loss of control. A composite measure of disordered eating will be calculated by averaging individual z-scores derived from these measures. We predict that higher levels of disordered eating will be associated with less weight loss 24 months following bariatric surgery. Weight: Weight will be measured with a calibrated digital scale with subjects dressed in light clothing and without shoes. Percent weight loss will be calculated from participants current weight (at each assessment point) as compared to their baseline weight. Participants with higher levels of impulsivity, psychopathology, and disordered eating are predicted to lose less weight at 24 months as compared to those with lower levels. Psychosocial Status: Medical Outcomes Study 36-Item Short Form Survey (SF-36)137: used to measure quality of life Impact of Weight on Quality of Life-Lite (IWOOL-Lite) 138: used to measure quality of life Dietary Intake: ASA-24: public-access, freely available (through the National Cancer Institute), web-based tool to obtain high-quality dietary intake data with minimal bias, making it a preferred tool for studying diet and disease associations.139 These 24-hour food recalls will be conducted at each time point for one weekday and one weekend day. Physical Activity: College Alumnus Survey (commonly known as the Paffenbarger Survey140): calculate self-reported leisure time physical activity kilocaloric expenditure per week. The frame of reference will be the past 6

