
months. This survey has excellent reliability and validity, including predictive validity for cardiovascular disease outcomes, and compares favorably to 7 day recall. (Note. We acknowledge that objective measures of physical activity have been found to be more reliable in bariatric samples.141 However, as change in physical activity is an outcome of secondary interest, we have elected to use a well-known self-report measure. We hypothesize that changes in quality of life, dietary intake, and physical activity will be associated with changes in weight. Social Support: The Medical Outcomes Study Social Support Survey is a brief, multidimensional, self-administered, social support survey that was developed for patients in the Medical Outcomes Study (MOS), a two-year survey that was developed for patients with chronic conditions. This survey was designed to explore various dimensions of functional social support, including emotional/informational support, tangible support, affectionate support, and positive social interaction. Sherbourne and Stewart (1991) found that the support measures are reliable (all Alphas 0.91), and are fairly stable over time. Selected construct validity hypotheses have been supported. Prevalence and Control of Chronic Diseases: 1) T2D will be identified using hemoglobin A1c (HbA1c) and glucose measurements obtained from fasting blood samples, and will be defined as HbA1c 6.5% and glucose 7.0 mmol/L (126 mg/dL), or use of antidiabetes medication.36 Prevalence will be calculated using number of participants with T2D as the numerator and total number of participants as the denominator. Controlled T2D, among individuals diagnosed with T2D, will be defined as HbA1c 7.0%.36 These labs are drawn as part of standard clinical care and the HbA1c and glucose results will be extracted from the EMR of enrolled participants. Participants will not be asked to have additional blood draws as part of the study. 2) Hypertension: systolic blood pressure (SBP) and diastolic blood pressure (DBP) will be measured using a Dinamap 9300XL monitor.. Using recently updated US guidelines, hypertension will be defined as SBP130 mm Hg, or DBP80 mm Hg, or use of antihypertensive medication.39 Prevalence will be calculated using number of participants with hypertension as the numerator and total number of participants as the denominator. Controlled hypertension, among individuals with hypertension, will be defined as SBP130 mm Hg and DBP80 mm Hg.39 Blood pressure is measured as part of standard clinical care. SBP and DBP will also be extracted from the medical record of enrolled participants from their preoperative testing with the bariatric surgery program as well as their postoperative follow up with the surgical team. Participants will have blood pressure measured as part of the study assessment. This blood pressure reading will be collected using a standardized protocol. Participants will be asked to remain seated for 5 minutes prior to the reading. Blood pressure will then be measured three times in a seated position with one minute rest between readings using the Dinamap 9300XL monitor. Healthcare Utilization: This information will be extracted from electronic medical records (EMRs) for the following services: primary care, hospitalizations, and emergency room visits. Total number of visits and number of visits to each service will be calculated for all-cause, mental health, T2D, and hypertension related, separately. Duration of stay will also be assessed.41,42 Based on previous experience of the research team, over 70% of participants will receive their non-bariatric care in the TU or Penn systems during the study. Therefore, we will be able to obtain utilization records through the EMR. However, to ensure complete data capture, we will also use a standardized and validated method employed in the Action for Health in Diabetes (Look AHEAD) study which assesses health services utilization using interviews at study visits.43 Medication Adherence: Among individuals with T2D and hypertension, medication adherence will be calculated, separately, using EMR data for pharmacy fills. We will use the prescription-based proportion of days covered (PDC) method to calculate adherence during the first and second year following surgery. PDC numerator will be defined as number of days with medication available to take between the date of the first medication fill during each time period (Year 1 and 2, separately) to the date of the last fill within the period, and the denominator will be the number of days between the date of the first and last fills during the period.44 Adherence will be defined as a PDC80%. In anticipation of missing EMR data on pharmacy fills, during the baseline, 6-, 12-, and 24-month study visits, we will administer the K-Wood-4 Medication Adherence Scale, a 4-item self-report questionnaire, to assess adherence and provide a way to validate results obtained from the EMR. Temple Health participants will have the option of completing the above assessments in English or Spanish. Participants whose surgery date is scheduled greater than 90 days after their baseline assessment (due to delays in scheduling surgery) may be asked to return to the clinic to complete a portion of the assessment. Participants will be asked to complete the ASA 24 hour dietary food recall and the impulsivity tasks (described above) within approximately 2-8 weeks prior to surgery in order to ensure that these data are within the appropriate time frame prior to surgery. We anticipate that this portion of this assessment will take approximately one hour to complete. If participants are willing to return to the clinic to complete these two portions of the assessment, they will be compensated \$25 for their time.

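### When surgery is delayed beyond 90 days, the return visit does not repeat weight, so the primary outcome can rest on a reference weight at least 5 weeks outside the planned window

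*Combined protocol and SAP*

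**What the plan says.** The primary outcome is given under Primary outcome variable(s) as "Specific Aim 1: weight change". The weight entry under Study Procedures defines the measure: "Percent weight loss will be calculated from participants current weight (at each assessment point) as compared to their baseline weight". The Analysis Plan models change in weight from baseline to months 6, 12 and 24, and names the Group x Time interaction as the main interest.

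Timing is set under Administration of Surveys and/or Process and repeated under Subject recruitment: "The first visit or baseline visit (Month 0) will occur within approximately 2-8 weeks of bariatric surgery". Late surgery has its own rule, in Administration of Surveys and/or Process and again in Procedures: "Participants whose surgery date is scheduled greater than 90 days after their baseline assessment (due to delays in scheduling surgery) may be asked to return". The content of that visit follows: "Participants will be asked to complete the ASA 24 hour dietary food recall and the impulsivity tasks". The stated purpose is to bring those data back inside the 2-8 week window. Attendance is voluntary and the scope is closed: "If participants are willing to return to the clinic to complete these two portions of the assessment".

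The documents name no other reference weight for these participants. Height and weight are reviewed from the surgery programme at screening, which comes before the baseline visit. The continuing record review lists diagnoses, psychiatric medication, appointment dates, and date and type of surgery, but not weight. The model adjusts for procedure, gender and time since surgery, not for the interval from baseline to surgery.

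**The concern.** The protocol accepts that some preoperative data become too old when surgery is delayed, and it refreshes two instruments for that reason. It does not refresh the one measurement that every value of the primary outcome depends on. Any weight lost or gained between the baseline visit and the operation is then counted as part of the postoperative result.

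Patients are also in a setting where weight may well move: "patients attend 3 to 6 monthly, preoperative weight management (MWM) sessions". If patients with more impulsivity or disordered eating lose less before surgery, their recorded loss would be lowered relative to the others, which leans toward the study's own hypothesis. For a patient who does return, the impulsivity predictor and the weight outcome would also start from different dates.

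**Working it through.** The documents give no figure on this point to reproduce, so the check has three parts: the age of the weight, the shift per patient, and where the shift enters the analysis.

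**Age of the reference weight.** The planned window is 2-8 weeks, or 14-56 days. The return rule starts above 90 days, so at day 91 at the earliest. 91 - 56 = 35 days, so the weight is at least 5 weeks past the upper limit. Between days 57 and 90 the baseline is already past the approximate limit and no repeat of any kind is planned.

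**Shift per affected patient.** Let *g* be the fraction of weight lost between the baseline visit and surgery (negative for a gain), and *L* the fraction lost relative to weight at surgery.

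- Observed loss = 1 - (1 - g)(1 - L)
- Shift = observed loss - L = g(1 - L)

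Inputs: L = 20-35%. This is the range in the Background, which is stated there for initial body weight; applying it to weight at surgery is an assumption. g = 3% and 5% are assumptions, because the documents give no preoperative weight change.

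| Preoperative change | L = 20% | L = 35% |
|---|---|---|
| 3% loss | +2.40 points | +1.95 points |
| 5% loss | +4.00 points | +3.25 points |
| 3% gain | -2.40 points | -1.95 points |

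Example: with L = 25% and g = 5%, observed loss = 1 - 0.95 × 0.75 = 28.75%, a shift of +3.75 points.

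**Group x Time interaction.** For absolute change, write W0 for baseline weight, Ws for weight at surgery and Wt for weight at follow-up. Then Wt - W0 = (Wt - Ws) + (Ws - W0). The last term is the same at months 6, 12 and 24, so with complete follow-up it drops out of any contrast over time. For percent loss the shift is g(1 - L), so only its variation with L remains. With g = 5% and L moving from 25% to 30%, that is 3.75 - 3.50 = 0.25 points per affected patient.

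**24-month group difference.** Here nothing cancels. If g is the same in both groups but the share delayed differs by D, the bias is D × g(1 - L). With g = 5% and D = 10-30 percentage points (both assumed), it runs from 0.10 × 3.25 = 0.33 to 0.30 × 4.00 = 1.20 points. The Secondary Aim 1 outcome is change in weight at 24 months, a single time point, so it is exposed in the same way.

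**The case against.** The strongest reply is that the test named as the main interest is the Group x Time interaction, and a fixed error in the baseline weight cancels from it exactly for absolute change and almost entirely for percent loss. That stands. It narrows the point to the 24-month comparison, which is what the protocol's predictions are about, and to Secondary Aim 1.

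Three stronger readings are tempting, and the documents do not support them.

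- *Out-of-date weights are common.* A reader might infer this from the Study duration section: "in many cases, patients receive all preoperative clearances months before their surgery date". That sentence concerns the time from clearance to surgery and explains why enrolment may exceed 24 months. It does not describe the gap from the baseline visit to surgery, which is separately tied to the operation date. The gap above 90 days is presented as a result of scheduling delay, and its frequency is not given.
- *The error is systematically related to the predictors.* No section links preoperative weight change or scheduling delay to impulsivity, eating behaviour or psychopathology. Attendance at weight management sessions does not show that weight moves during a delay. The link is plausible and no more.
- *The result is biased by 2-4 points.* That is the shift for one affected patient under assumed inputs. The effect on a group estimate is diluted by unaffected patients.

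It can also be said that staff may weigh returning patients anyway. The plan neither says so nor says that such a weight would be used.

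**Conclusion.** The gap is real. Followed as written, the plan leaves participants delayed beyond 90 days with a reference weight at least 5 weeks outside the planned window, even where other measures are refreshed.

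Its size cannot be established from the documents. The illustration is about 2-4 percentage points per affected patient, resting on an assumed 3-5% preoperative change and 20-35% loss from weight at surgery. Any bias in a group comparison depends further on how many patients are delayed and on whether delay or preoperative change differs by predictor level, both unknown. The interaction test is largely protected; the 24-month group difference and the Secondary Aim 1 outcome are not. The matter is worth correcting because the remedy is cheap and concerns the reference value of the primary outcome.

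**What to change.** - Add weight to the existing return visit, measured on the study scale under the conditions already set for study weights (calibrated digital scale, light clothing, no shoes), and make it the reference weight for those participants.
- Because the visit is optional, state a fallback: for a delayed participant who does not return, take from the chart the last bariatric-programme weight within 8 weeks before surgery.
- Leave the baseline weight of on-time participants unchanged. Replacing everyone's baseline with a mixture of study, clinic and surgery-day weights would give up a standardised measurement where there is no need to.
- Run a sensitivity analysis that uses the baseline-visit weight for all participants.

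The cost is a few minutes at a visit that is already planned and paid ($25) and one extra chart field, which needs a protocol change because weight is not in the listed record extraction. A few reference weights will come from a clinic scale; the sensitivity analysis shows whether the choice of reference weight matters.
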